*** Purpose, Study Procedures, Background ***

Original Protocol Number (e.g., 07-226H)

Title (Please indicate if the protocol title is different from the proposal title)

Does Dapagliflozin Augment The Favorable Adaptation To Endurance Exercise Training?
Clinical Research Protocol Title: Dapagliflozin Augments The Favorable Adaptation To Endurance Exercise Training

Complete Sections 1 - 16. Specify N/A as appropriate. Do not leave any required sections blank.

1. Purpose of the study

a) Provide a brief lay summary of the project in <200 words. The lay summary should be readily understandable to the general public, and is, for example, what would be released to a newspaper if requested.

Exercise is frequently prescribed as a favorable lifestyle intervention to prevent/reverse type 2 diabetes. It is also prescribed in addition to concurrent pharmacological treatment, such as metformin. Recent data (animal and human) suggest that metformin may attenuate the favorable benefits of exercise training. In light of the physiological mechanism of Dapagliflozin (sodium-glucose co-transporter 2 (SGLT2) inhibition), one might speculate that rather than inhibit, it will augment the favorable adaptations to exercise training.

b) **What does the Investigator(s) hope to learn from the study?**

We wish to learn if Dapagliflozin augments the favorable adaptation to endurance exercise training in previously sedentary overweight/obese adult humans.

c) **Proposed Start Date (may not precede IRB approval date):**

On receipt of IRB approval (and FDA approval of IND application).

2.

Protocol Title: Does Dapagliflozin Augment The Favorable Adaptation To Endurance Exercise Training?
Clinical Research Protocol Title: Dapagliflozin Augments The Favorable Adaptation To Endurance Exercise Training

Protocol Type: Biomedical

Date Submitted: 11/01/2018

Approval Period: 11/06/2018-11/05/2019

Important Note: This Print View may not reflect all comments and contingencies for approval. Please check the comments section of the online protocol.
Questions that appear to not have been answered may not have been required for this submission.
Please see the system application for more details.

Study Procedures (If this is a student project, the methods section of the thesis or dissertation proposal must be attached in section #16 - Attachment section.)

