a) In lay language, describe all the procedures, from screening through end-of-study, that the human subject must undergo in the research project, including study visits, drug treatments, randomization and the procedures that are part of standard of care. Please note: Do NOT respond "See Attachment Section." If you would like to add tables, charts, etc., attach those files in the Attachment section (#16).

OVERVIEW

This is a randomized, placebo-controlled, double blind, repeated measures study. 30 sedentary adults will be recruited for participation and randomly assigned to one of two 12-week treatments: 1) supervised endurance exercise training 4 days per week plus daily oral administration of Dapagliflozin; 2) supervised endurance exercise training 4 days per week plus daily oral administration of placebo. Prior to and following completion of the treatment the following dependent variables will be quantified: a) maximal aerobic capacity; b) substrate utilization during standardized low-moderate intensity exercise; c) skeletal muscle aerobic enzyme activity; d) body composition; and, e) oral glucose tolerance, fasting glucose and insulin resistance.

Study participants will report to the Human Performance/Clinical Research Laboratory (HPCRL) on 51 separate occasions:

Visit 1: study participants will undergo screening: medical history, 12-lead electrocardiogram and blood pressure assessment at rest and during incremental exercise to volitional exhaustion, blood sampling, and measurement of body composition.

Visit 2: maximal oxygen uptake will be measured.

Visit 3: the metabolic response to standardized exercise will be determined.

Visit 4: an oral glucose tolerance test will be performed, and then skeletal muscle will be sampled.

Visits 5-48: 12 weeks of supervised exercise training. Concurrent with these visits, research participants will ingest, on a daily basis, either Dapagliflozin or placebo.

Visit 49: maximal oxygen uptake and body composition will be measured.

Visit 50: the metabolic response to standardized exercise will be determined.

Visit 51: an oral glucose tolerance test will be performed, and then skeletal muscle will be sampled.

DETAILED DESCRIPTION OF STUDY PROCEDURES

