*** Subject Population (a-g) ***

8.

Subject Population - In the space below, please detail the participants that you are requesting to recruit (include requested participant number and description of each group requested). (Input N/A if not applicable)

a) **Requested Participant Description (Include number of participants that you plan to study and description of each group requested, if applicable).**

We plan on enrolling 60 participants with estimation that 50% will screen out or not complete the study. We plan to complete the study in 30 overweight/obese adult volunteers (men and women).

b) **What is the rationale for studying the requested group(s) of participants?**

Adults who are overweight/obese are at the greatest risk of developing type 2 diabetes, thus overweight/obese adults potentially have the most to gain should the outcome of the study prove

Protocol Title: Does Dapagliflozin Augment The Favorable Adaptation To Endurance Exercise Training?
Clinical Research Protocol Title: Dapagliflozin Augments The Favorable Adaptation To Endurance Exercise Training

Protocol Type: Biomedical

Date Submitted: 11/01/2018

Approval Period: 11/06/2018-11/05/2019

Important Note: This Print View may not reflect all comments and contingencies for approval. Please check the comments section of the online protocol. Questions that appear to not have been answered may not have been required for this submission. Please see the system application for more details.

favorable. Inclusion of adults already diagnosed with diabetes might complicate the interpretation of the data; that is, as a consequence of the patho-physiology associated with diabetes, the response to exercise training with or without Dapagliflozin may differ in adults with diabetes compared with adults who are diabetes free.

c) If applicable, state the rationale for involvement of potentially vulnerable subjects to be entered into the study, including minors, pregnant women, economically and educationally disadvantaged, or decisionally impaired subjects. Specify the measures being taken to minimize the risks and the chance of harm to the potentially vulnerable subjects.

Potentially vulnerable subjects will not be studied.

d) If women, minorities, or minors are not included, a clear compelling rationale must be provided. Examples for not including minors: disease does not occur in children; drug or device would interfere with normal growth and development; etc.

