Clinical Research Protocol Title: Dapagliflozin Augments The Favorable Adaptation To Endurance Exercise Training

Protocol Type: Biomedical

Date Submitted: 11/01/2018

Approval Period: 11/06/2018-11/05/2019

Important Note: This Print View may not reflect all comments and contingencies for approval. Please check the comments section of the online protocol.
Questions that appear to not have been answered may not have been required for this submission.
Please see the system application for more details.

11/29/2017	CONTINUING REVIEW 3 FORM APPROVED	Y	Y
11/01/2018	CONTINUING REVIEW 4 FORM CREATED		
11/01/2018	CONTINUING REVIEW 4 FORM SUBMITTED	Y	
11/06/2018	CONTINUING REVIEW 4 FORM APPROVED	Y	Y

Methods of statistical analyses

Two-way analysis of variance (before training *vs.* after training, and Dapagliflozin *vs.* Placebo) with repeated measures on one factor (before *vs.* after) are used to examine differences in primary outcomes resulting from exercise training and/or drug treatment. Multiple comparisons of factor means will be performed using the Newman-Keuls test.

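### Newman-Keuls, applied to the four arm-by-time means with no interaction gate, does not hold familywise error: about 7-9% rather than 5% if training works and the drug adds nothing

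*Combined protocol and SAP*

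**What the plan says.** The statistical plan is two sentences under Methods of statistical analyses, at the end of the document after the Event History table. The first gives a two-way ANOVA, time (before, after) by arm (dapagliflozin, placebo), with time as the repeated factor. These analyses "are used to examine differences in primary outcomes resulting from exercise training and/or drug treatment". The second reads "Multiple comparisons of factor means will be performed using the Newman-Keuls test".

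The text does not state a significance level, the error term for the comparisons, which means are compared, or whether comparisons depend on a significant interaction.

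The Overview under Study Procedures gives the design. Participants are "randomly assigned to one of two 12-week treatments", and on timing, "Prior to and following completion of the treatment the following dependent variables will be quantified". Item 8a of Subject Population plans for 30 completers out of 60 enrolled. The lay summary gives the hypothesis: given the drug's mechanism, "one might speculate that rather than inhibit, it will augment the favorable adaptations to exercise training".

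**The concern.** Each factor has two levels, so a comparison of its two marginal means only repeats the ANOVA F test. A multiple-comparison procedure has work to do only on the four cells: drug-before, drug-after, placebo-before and placebo-after.

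Newman-Keuls is weakest when equal means form well-separated pairs. If training works and the drug adds nothing, the two before means are equal, the two after means are equal, and training separates the pairs. The larger ranges are rejected because of training, and each drug-placebo pair is then tested at the full unadjusted level.

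The four cells also mix two kinds of contrast. Before-after differences are within person and drug-placebo differences are between persons, so their error variances differ. One procedure with no stated error term covers both. At stake is the reliability of any pairwise drug-placebo difference reported from this analysis.

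**Working it through.** **Inputs from the documents.** Two arms, two time points, 30 planned completers. The only planning figure that can be reproduced is enrolment: 30 / (1 - 0.5) = 60, which matches. There is no stated error rate to reproduce.

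**Assumptions, because the documents give no figure.** Level 5% two-sided; 1:1 allocation, so 15 completers per arm; normal data with equal variances; no drug effect; training effect 0, 0.5, 1 or 3 SD; before-after correlation (rho) 0 to 0.9.

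**Step 1: limit in theory.** With the pairs well separated and the time points independent, two null pairs are each tested at 5%: 1 - 0.95 x 0.95 = 0.0975, or 9.75%.

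**Step 2: simulation.** 40,000 trials per setting, with step-down studentized-range critical values on the four cell means. Before-after pairs use the within-person mean square. Drug-placebo pairs use the pooled between- plus within-person mean square with Satterthwaite degrees of freedom. Percentage of trials with a false drug-placebo difference:

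| Training effect, pair(s) counted | rho 0 | 0.5 | 0.7 | 0.8 | 0.9 |
|---|---|---|---|---|---|
| 1 SD, either pair | 9.0 | 8.4 | 8.4 | 7.6 | 6.9 |
| 3 SD, either pair | 9.7 | 9.1 | 8.0 | 7.7 | 7.2 |
| 1 SD, after training only | 4.6 | 4.6 | 4.9 | 4.9 | 4.9 |
| 3 SD, after training only | 5.0 | 5.0 | 4.8 | 4.9 | 5.0 |

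Across the same correlations, the either-pair rate is 3.1-5.2% at 0.5 SD and 1.7-2.8% with no training effect.

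**Step 3: source of the excess.** At 1 SD and rho 0.5, the either-pair rate is 8.42% and the after-training rate 4.57%. The difference, 8.42 - 4.57 = 3.85 points, is trials in which only the baseline pair is falsely significant. At rho 0.9 it is 6.91 - 4.91 = 2.00 points.

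**Step 4: error term.** Write the variance of one measurement as S2. The correct variance of a drug-placebo cell difference is 2 x S2 / n. The within-person residual has expectation S2 x (1 - rho), so using it shrinks the standard error by sqrt(1 - rho): 0.71, 0.55, 0.45 and 0.32 at rho 0.5, 0.7, 0.8 and 0.9. A normal approximation to the resulting error of one comparison, 2 x Phi(-1.96 x sqrt(1 - rho)), gives about 17%, 28%, 38% and 54%. The simulation at 1 SD gives about 16%, 27%, 37% and 52% for the after-training pair, and 27%, 40%, 50% and 64% for either pair.

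**Step 5: alternatives under the same null.** The first four use a 3 SD training effect and rho 0 to 0.9.
- Arm-by-time interaction alone: 4.9-5.2%.
- Baseline-adjusted ANCOVA on the after value: 4.9-5.1%.
- Bonferroni over the two drug-placebo pairs, correct error: 3.7-4.8% for either pair.
- Newman-Keuls only after a significant interaction: 0.7-3.2% with the correct error, 3.3-4.6% with the residual.
- Holm over the four non-diagonal pairs, correct error (1-2 SD, rho 0.5-0.9): 3.3-4.7%, against 6.8-8.9% for Newman-Keuls in the same settings.

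**The case against.** The strongest reply is that the plan never says the four cells are compared. It says factor means, and if marginal means are intended there is one comparison per factor and no inflation. That is a possible reading, and the four-cell reading is an inference. But the marginal reading leaves the sentence with nothing to do, so the text needs to change either way.

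A reader might infer that a post-training drug-placebo difference carries an inflated error rate in any event. The documents do not support that. With the correct error term this comparison stays near 5%, and the excess arises at baseline, before any drug is given, where a false difference could hardly be reported as a drug effect.

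A reader might also take 27-64% as the size of the problem. That requires the within-person residual for between-person pairs. The text does not say so, and the standard analysis of this mixed design has separate error terms. Silence is not a plan to use the wrong one, so these figures are a conditional risk only.

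The ANOVA is named before the comparisons, which would fit a gated sequence, and a gate would bring the either-pair rate below 5% with either error term. No gate is written. Two sponsor's protocol files are listed under Attachments but are not part of the documents reviewed; a gate, level or error term may be stated there.

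**Conclusion.** The point holds conditionally. If Newman-Keuls is applied to the four arm-by-time means without an interaction gate, the chance of at least one false drug-placebo difference is about 7-9% per outcome for a training effect of 1 SD or more and rho 0.5-0.9, and up to about 10% at rho 0. At 0.5 SD or below there is essentially no inflation. This rests on a 5% two-sided level, 15 completers per arm, normality and equal variances, none of which is stated.

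Two further inferences should not be drawn. Training effective with no drug effect is the null against which a false-positive rate is judged; it is not what the trial expects, since the hypothesis is augmentation. Nor does the plan breach an error rate of its own, because it states none.

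The unstated error term matters because it decides whether the post-training comparison has an error near 5% or, at 1 SD, about 16-52%. It should be fixed in the text.

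**What to change.** Replace the Newman-Keuls sentence with:

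> The arm-by-time interaction is the test of the drug effect. Follow-up comparisons are limited to before vs after within each arm (within-person error) and drug vs placebo after training (pooled between- plus within-person error, Satterthwaite degrees of freedom), Holm-adjusted as one family of three. The baseline drug-placebo pair and the diagonal pairs are not tested.

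State the significance level alongside it. The interaction test holds about 5% under the null examined here. Holm controls the family of three at the chosen level by construction, and dropping the baseline pair removes the source of the excess.

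The cost is this short replacement text, a few lines of code and slightly fewer significant pairs. The continuing-review form reports that recruitment and interventions are finished and only data analysis remains, so the change must be recorded as made after data collection.
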